10.2.3.14 Correlation between RWS with weight and dynamometry

Spearman correlation coefficient, with 95% CI and p-value, will be calculated between the average total RSA Q1-Q5 with 500 g wrist weight and the following dynamometry measures at baseline and each post-baseline visit, by treatment group:

- Average shoulder abductor strength (kg)
- Average hand grip strength (kg)
- Total average muscle strength (kg)

This analysis will be repeated for the change from baseline and relative change from baseline in the average total RSA Q1-Q5 with 500 g wrist weight versus change from baseline and relative change from baseline in each dynamometry measure, respectively, at each post-baseline visit, by treatment group.

[figure not shown]
A corresponding scatterplot will be presented for each correlation.

10.2.3.15 Correlation between RWS with weight and patient-reported outcomes

Spearman correlation coefficient, with 95% CI and p-value, will be calculated between the average total RSA Q1-Q5 with 500 g wrist weight and the following patient reported outcomes at baseline and each post-baseline visit, by treatment group:

- Neuro-QoL-UE
- Sub-Neuro-QoLUE

- PGIC, [REDACTED]

10.3 SAFETY ANALYSES

The safety analysis will consist of an assessment of adverse events, serious adverse events, clinical laboratory tests, electrocardiograms (ECGs), vital signs, and physical examinations.

The safety analyses will be based on the Safety Analysis Set and summarized by treatment group. Safety data collected at unscheduled visits and local laboratory data will be excluded from by-visit summaries using descriptive statistics for continuous variables, but included in listings and in identifying min/max/worst results for laboratory data analyses, etc.

10.3.1 Treatment-emergent adverse events

The number and percentage of patients with at least one TEAE in the following categories will be presented by treatment group:

- Any TEAE
- TEAE related to study drug
- TEAE with a CTCAE grade of 3 or higher
- TEAE with a CTCAE grade of 3 or higher, related to study drug
- TEAE leading to discontinuation of study drug
- TEAE leading to withdrawal from study
- TEAE with an outcome of death
- TEAE with an outcome of death, possibly related to study drug
- TEAE of special interest (AESI)

The number and percentage of patients with at least one TEAE will be summarized by SOC and PT, by treatment group. The total number of TEAEs observed within each category will be reported.

The number and percentage of patients with at least one TEAE will be summarized by maximum CTCAE grade. Maximum CTCAE grade will also be presented by SOC and PT, by treatment group.

The number of TEAEs will be presented by relationship (5 levels: definitely related, probably related, possibly related, unlikely related, not related) to study drug, by treatment group. Numbers and percentages of patients with at least one TEAE will be summarized by highest level of relationship, overall and by SOC and PT.

All AEs will be listed. Listings will be presented by FSHD type and treatment. They will include patient age, sex, race, country, SOC, PT, AE description as reported in eCRF, start, and stop dates and study days, duration in days, outcome (Recovered/Resolved, Recovering/Resolving, Not recovered/Not resolved, Recovered/Resolved with sequelae, Fatal), severity (Mild, Moderate, Severe, Life-threatening), action (Drug interrupted, Drug withdrawn, Not applicable, Other (Specify)), relationship, whether it resulted in study discontinuation, and seriousness/if yes, SAE criteria. TEAEs will be flagged.

10.3.2 Deaths and serious adverse events

The number and percentage of patients with at least one SAE in the following categories will be presented:

- Any SAE
- SAE related to study drug

The number of SAEs will be presented by treatment group. Numbers and percentages of patients with at least one SAE will be summarized by SOC and PT. All SAEs will be listed in the same way as AEs.

Deaths will be listed by FSHD type and treatment group, and include date of death, primary cause of death, relatedness and whether an autopsy was performed.

10.3.3 Adverse events leading to discontinuation of investigational product and/or withdrawal from the study

The number of TEAEs leading to discontinuation of study drug will be presented by treatment group. Numbers and percentages of patients with at least one TEAE leading to study drug discontinuation will be summarized by SOC and PT, and also by maximum CTCAE grade.

The number of TEAEs leading to withdrawal from the study will be presented by treatment group. Numbers and percentages of patients with at least one TEAE leading to withdrawal from the study will be summarized by SOC and PT, and also by maximum CTCAE grade.

All AEs leading to discontinuation of study drug will be listed in a single listing, in the same way as AEs. AEs leading to withdrawal from study are flagged in the AE listing.

10.3.4 Other adverse events of special interest

The number of AEs identified as AESIs will be presented by treatment group. Numbers and percentages of patients with at least one such AESI will be presented. AESIs will be listed in the same way as AEs.

The number and percentage of patients with laboratory tests that potentially flag a drug-induced liver injury (DILI):

- (ALT \geq 3ULN; Total bilirubin \geq 2ULN; and ALP $<$ 2ULN)
- (AST \geq 3ULN; Total bilirubin \geq 2ULN; and ALP $<$ 2ULN)

will be presented for each test type, treatment group and visit; the number and percentage of patients with a potential DILI will be presented by treatment group and visit. Denominators for percentages are the number of patients in treatment group with normal baseline result and non-missing result for given parameter and visit. ALT, AST, total bilirubin, and ALP will be listed for each potential DILI, by treatment group, patient, and visit. In addition, the number and percentage of patients with ALT \geq 3ULN, AST \geq 3ULN and total bilirubin \geq 2ULN will be presented separately for each treatment group and visit. These results will be listed, including the result dividing by the ULN.

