7.5. ADVERSE EVENTS OF SPECIAL INTEREST

An AESI (serious or non-serious) is one of scientific and medical concern for which ongoing monitoring and rapid communication by the Investigator to the Sponsor is appropriate. If an AE or the abnormality is an AESI, the event should be reported on an SAE form, regardless of seriousness, and captured in the safety database. Non-serious AESIs will not be reported to the Regulatory Authorities unless required.

Adverse events of special interest for this study include liver tests that meet the criteria for potential drug-induced liver injury, in accordance with the US FDA "Guidance for Industry-Drug-Induced Liver Injury: Premarketing Clinical Evaluation."

Liver Tests and Stopping Criteria

The following 3 laboratory value criteria must be met for potential DILI, or "Hy's Law":

- An elevated ALT or aspartate aminotransferase laboratory value that is $\geq 3 \times$ ULN
- An elevated total bilirubin laboratory value that is $\geq 2 \times$ ULN
- An alkaline phosphatase laboratory value that is $< 2 \times$ ULN

Study drug should be discontinued for patients who meet the laboratory criteria for potential DILI as a result of within-protocol specific testing or unscheduled testing. This AESI must be reported to the Sponsor within 24 hours of awareness. Further safety steps should be taken to closely observe and follow the event until resolution. These steps include, but are not limited to:

- Making every reasonable attempt to have the patient return to the clinic within 24 hours for repeat liver enzyme tests.
- Obtaining a more detailed history of symptoms and prior or concurrent disease, concomitant medication use, alcohol use, recreational drug use, and special diets.
- Repeating liver enzyme and serum bilirubin tests twice weekly. Frequency of retesting can decrease to once a week or less if abnormalities stabilize and the patient is asymptomatic.
- Obtaining viral hepatitis serology.
- Considering liver imaging and/or hepatology consultation.

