9.5 ASSESSMENT TIME WINDOWS

9.5.1 Definition of permissible time windows

All study visits from baseline to Week 48 have a window of +/- 7 days inclusive in the schedule of assessments. For the purpose of efficacy, PK and safety analysis, visit windows will be treated as continuous, from the midpoint between two consecutive study visits:

Visit	Window
Screening	From enrollment to randomization

REACH TRIAL

Baseline	Day of randomization, or date of last non-missing value obtained prior to the first dose of study treatment.
Week 4	Days 15 to 56
Week 12	Days 57 to 126
Week 24	Days 127 to 210
Week 36	Days 211 to 294
Week 48	Days 295 to the earliest of Day 357 or Day of OLE Study Drug Dose 1

Data collected after the first dose of study treatment up to and including Day 14 will be treated as unscheduled. Where there is more than one measurement within a visit window, the visit closest to the target visit date will be included for analysis. Where two visits are equidistant to the target visit date, the later visit will be included for analysis. Data collected during visits that are excluded because another is closer to the target visit date will be treated as out-of-window observations.

Efficacy and PK data from both scheduled and unscheduled visits and from Early Termination visit will go through the above windowing process. Similarly, safety data from scheduled visits, from Early Termination visit and from Safety Follow-up visit will go through the above windowing process.

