9.5.2 Methods for handling out-of-window observations

Out-of-window observations will be treated as unscheduled visits. Unscheduled visit data will be excluded from by-visit summaries, but included in the following: efficacy analyses through windowing (see 9.5.1); listings; and in identifying min/max/worst results for laboratory data analyses, etc.

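### The separate counts of ALT or AST at or above 3×ULN and total bilirubin at or above 2×ULN are by visit only, so an isolated elevation seen only at an unscheduled test enters no ULN-multiple count

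*SAP*

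**What the plan says.** SAP 10.3.4 plans three kinds of liver output.

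- **AESI counts.** "The number of AEs identified as AESIs will be presented by treatment group", and "Numbers and percentages of patients with at least one such AESI will be presented". SAP 9.3.4.1 defines the AESI from laboratory values: ALT or AST ≥3×ULN, with total bilirubin ≥2×ULN and ALP <2×ULN. No visit dimension is given. The AESI appears again in the TEAE overview of 10.3.1.
- **Potential DILI.** "the number and percentage of patients with a potential DILI will be presented by treatment group and visit".
- **Single analytes.** The numbers and percentages with ALT ≥3×ULN, AST ≥3×ULN and total bilirubin ≥2×ULN "will be presented separately for each treatment group and visit". These results are also listed, with each value divided by its ULN.

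Three rules decide which results reach a by-visit table.

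- SAP 9.5.1: "safety data from scheduled visits, from Early Termination visit and from Safety Follow-up visit will go through the above windowing process". Efficacy and PK data from unscheduled visits are windowed; unscheduled safety data are not named.
- SAP 9.5.2: "Unscheduled visit data will be excluded from by-visit summaries", with no limit on the type of summary.
- SAP 10.3: "Safety data collected at unscheduled visits and local laboratory data will be excluded from by-visit summaries using descriptive statistics for continuous variables". Both 9.5.2 and 10.3 keep these data for listings and for worst-value laboratory analyses.

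Protocol 7.5 recognises that a patient may meet the potential-DILI criteria "as a result of within-protocol specific testing or unscheduled testing".

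**The concern.** Hepatotoxicity is the first of the two important potential risks in Protocol 1.3.2, and potential DILI is the trial's only AESI. The single-analyte counts are where a modest liver signal would show first, because the combined criterion is much rarer. Followed as written, the SAP can leave an off-schedule elevation out of those counts.

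Even for scheduled results, by-visit counts do not give an incidence. A patient elevated at Weeks 12 and 24 is counted in both columns, so the columns cannot be added. Protocol 1.3.2.1 reports earlier experience as a proportion of subjects with ALT ≥3×ULN, and no planned table gives a figure in that form.

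**Working it through.** The documents state no figure for this point, so there is none to reproduce. The check is a trace of each liver output against the inclusion rules, followed by a calculation of scale.

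**Step 1. Where can an isolated elevation from an unscheduled test appear?**

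| Output (SAP section) | Scale | Visit-bound? | Isolated unscheduled elevation included? |
|---|---|---|---|
| ALT, AST, bilirubin counts (10.3.4) | ULN multiple | Yes | No: no window (9.5.1), excluded (9.5.2) |
| Potential DILI by visit (10.3.4) | ULN multiple, combined | Yes | No |
| AESI counts (9.3.4.1, 10.3.1, 10.3.4) | ULN multiple, combined | No | No; a full combined-criterion case can be |
| Shift to highest category (10.3.5) | Low/normal/high | No | Yes, but only as high |
| TEAE tables (10.3.1) | Preferred term, CTCAE grade | No | Only if judged clinically significant and recorded as an AE (Protocol 6.1.5, 7.7) |
| Listings (10.3, 10.3.4) | Value divided by ULN | No | Yes |

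In the shift table, 1.1×ULN and 8×ULN fall in the same category, so it cannot stand in for a 3×ULN count.

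**Step 2. How does the SAP treat other safety measures?** SAP 10.3.7 categorises each patient's maximum on-treatment QTcF. SAP 10.3.6 uses each patient's minimum and maximum on-treatment vital signs. The liver analytes have no per-patient maximum on the ULN scale.

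**Step 3. How much time lies between scheduled tests?** Serum chemistry is scheduled on Study Days 1, 28, 84, 168, 252 and 336 (Protocol Table 7). The gaps are 27, 56, 84, 84 and 84 days. Apart from early-termination or follow-up visits, a liver test within a gap and outside the ±7-day visit window is unscheduled.

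**Step 4. How many cases are expected?** Inputs: about 115 patients per arm (Protocol 3.1.1); ALT ≥3×ULN in 0.9% on losmapimod and 0.5% on placebo across 11 studies, and in 8/391 = 2% on losmapimod in the NSTEMI study (Protocol 1.3.2.1).

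- Losmapimod at 0.9%: 115 × 0.009 = 1.0 patient; chance of at least one = 1 − 0.991^115 = 0.65.
- Losmapimod at 2%: 115 × 0.02 = 2.3 patients; chance of at least one = 1 − 0.98^115 = 0.90.
- Placebo at 0.5%: 115 × 0.005 = 0.6 patient; chance of at least one = 1 − 0.995^115 = 0.44.

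One omitted losmapimod patient is 1/2.3 = 43% to 1/1.035 = 97% of the expected count. It is also 1/115 = 0.87 percentage points, more than the earlier difference between arms of 0.9 − 0.5 = 0.4 points.

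**Step 5. How many would be omitted?** This cannot be calculated. A patient is lost through table design only if the elevation was measured off schedule and was not also present at a scheduled test. The documents give no rate of off-schedule testing.

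**The case against.** A reader might infer that every liver table is by visit and that any elevation between visits is counted nowhere on the ULN scale. The documents do not support that. The AESI summaries are ULN-based and have no visit limit, so a between-visit case meeting the full combined criterion can be counted there. What remains open is that the SAP does not say whether unscheduled or local results feed that derivation. The repeat testing in Protocol 7.5 concerns patients who already meet the combined criterion, so it is not evidence that isolated elevations will often be found off schedule.

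A reader might also infer that local laboratory results are barred from these counts. The only rule that names them, in SAP 10.3, covers by-visit descriptive statistics for continuous variables, and the liver counts are categorical. Their status is unclear. The unscheduled-visit point does not depend on it: it rests on 9.5.1 and 9.5.2.

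Nor do omitted peaks reach listings alone. They also enter the shift table as high and, if judged clinically significant, the AE tables.

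A further temptation is to use visit-overlap figures as a loss rate. With onset uniform over 48 weeks and visits at Weeks 4, 12, 24, 36 and 48, an elevation lasting 2, 4 or 8 weeks (assumed durations) overlaps a visit with probability 10/48 = 21%, 20/48 = 42% or 36/48 = 75%. The complement is not the share lost to table design, because an elevation nobody measures is missed under any layout.

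Two practical objections have weight. With one or two expected cases, a reader can count patients from the listing by hand. And SAP Appendix A refers the table shells to a separate file, which may already contain an overall row. Neither settles the matter: a between-arm summary of the main potential risk should not depend on a hand count, and the SAP text does not specify such a row.

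**Conclusion.** The concern holds for the single-analyte counts. As the SAP is written, an isolated ALT or AST ≥3×ULN or total bilirubin ≥2×ULN seen only at an unscheduled test is in no ULN-multiple count, and no table gives a once-per-patient incidence over the treatment period. It does not extend to full combined-criterion cases, which the AESI summaries can capture, subject to the unstated data source. Exclusion of local results from the categorical counts is a possible reading, not a stated rule.

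The expected number is small, about 1.0 to 2.3 losmapimod patients for ALT, assuming 115 per arm and that earlier rates carry over; the 2% comes from an NSTEMI population. One omission would therefore be visible, but the number of omissions cannot be estimated. The comparison with 0.9% and 0.5% is also limited, because the protocol does not say whether those proportions included unscheduled results. This is a cheap improvement to the tables. It leaves the analysis of efficacy and all clinical rules unchanged.

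**What to change.** In SAP 10.3.4:

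1. Add an any-time post-baseline (worst value) row per treatment group for ALT ≥3×ULN, AST ≥3×ULN, total bilirubin ≥2×ULN and potential DILI. Count each patient once. Include unscheduled and local laboratory results, each divided by its own laboratory's ULN.
2. State the denominator for that row, since the one now given in 10.3.4 is tied to a visit.
3. State that the same results feed the AESI derivation in 9.3.4.1, and whether 9.5.2 and the local-laboratory sentence in 10.3 apply to categorical liver counts.
4. Keep the by-visit tables as supportive.

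The cost is a few table rows and two or three sentences. No new assessments are needed: Protocol 6.1.5 already requires local results that change management or are clinically significant to be entered in the eCRF, and Protocol 12.3 already asks sites for the normal ranges of local laboratories.

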10.3.5 Clinical laboratory evaluations

Laboratory data (hematology, biochemistry, and urinalysis) will be presented as follows:

For each timepoint (baseline, weeks 4, 12, 24, 36 and 48, and the safety follow-up visit) absolute values and change from baseline will be summarized with standard summary statistics (see Section 8.1), by treatment group.

For the following hematology (hemoglobin, red blood cell count, hematocrit, total white blood cell count, # lymphocytes, neutrophils, basophils, eosinophils, and platelet count), biochemistry (total bilirubin, alkaline phosphatase, aspartate aminotransferase, alanine aminotransferase, gamma-glutamyltransferase), and urinalysis (glucose, blood and protein) parameters: shift from baseline will be tabulated for all patients with a baseline value as well as at least one post-baseline measurement, by treatment group: the number and percentage of patients at baseline classified as low, normal or high and overall will be presented; and the shift from baseline category to (a) lowest post-baseline category; and (b) highest post-baseline category. For parameters which have classifications in both the high and low direction, these will be summarized separately.

Hematology, biochemistry and urinalysis data will be presented in separate listings, by treatment group and FSHD type. Each listing will present patients' data by visit. Patients' 3 highest and 3 lowest results outside of the normal range for each variable will be flagged in the listings. Data from unscheduled visits and any early termination (ET) visit will be included in this assessment of low and high results.

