1.3.5.1. Effects on Serum Creatinine

A small increase in (model-adjusted geometric mean) serum creatinine in the combined losmapimod group compared to placebo at Week 12 was noted in Study PM1111810 (ratio 1.07 [95% CI: 1.02, 1.11]). Retrospective statistical analyses for creatinine levels in three other Phase 2 studies demonstrated similar trends (model-adjusted geometric mean ratio: 1.01 to 1.07 at Week 12). This increase appeared to attenuate with continued therapy (to Week 24 in chronic obstructive pulmonary disease) as well as with discontinuation (2 weeks post-treatment in acute coronary syndrome). There was no increase in the incidence of renal insufficiency or related adverse events.

There were no clinically relevant changes in serum creatinine or changes in estimated glomerular filtration rate observed in Fulcrum losmapimod clinical studies.

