5.8. PRIOR AND CONCOMITANT THERAPY

Use of all concomitant medications taken within 28 days before screening through the safety follow-up visits will be recorded in the patient's eCRF. The minimum requirement is that drug name and the dates of administration are to be recorded. This will include all prescription drugs, herbal products, vitamins, minerals, and over-the-counter medications. Any changes in concomitant medications also will be recorded in the patient's eCRF.

Any concomitant medication deemed necessary for the welfare of the patient during the study may be given at the discretion of the Investigator. However, it is the responsibility of the Investigator to ensure that details regarding the medication are recorded in full in the eCRF.

The use of the following medications is restricted or prohibited in this study:

- Vaccination with a live attenuated vaccine from 6 weeks prior to randomization until the safety follow-up visits.
- Patients who are on drug(s) or supplements that may affect muscle function, as determined by the Investigator, or that are included in the list of drugs presented in [Appendix 3](#) must be on a stable dose of that drug(s) or supplement for at least 3 months prior to the first dose of study drug and remain on that stable dose for the duration of the study. Changes to the dose or treatment discontinuation during the study can only be done for strict medical reasons by the treating physician with clear documentation and notification to the Sponsor. Treatment with a statin can be initiated during the study if it is medically required. In this case, preference should be given to hydrophilic statins (e.g., pravastatin, rosuvastatin, fluvastatin) over lipophilic statins (e.g., simvastatin, atorvastatin, lovastatin.) Particular attention should be paid to creatine phosphokinase (already part of the laboratory safety monitoring) in patients who start treatment with a statin during the study.

Subjects who take concomitant medications that are OAT1/OAT3 substrates and have a narrow therapeutic index may need to have their blood levels monitored for levels of the OAT1/OAT3 substrates after losmapimod dosing (see [Appendix 4](#)).

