Blood and other biological samples will be collected for the clinical laboratory tests in [Table 6](#).

Table 6: Protocol-Required Laboratory Tests

Serum chemistry	Glucose, sodium, potassium, calcium, inorganic phosphate, total protein, albumin, blood urea nitrogen, creatinine, total bilirubin, direct bilirubin*, alkaline phosphatase, aspartate aminotransferase, alanine aminotransferase, gamma-glutamyltransferase, creatine phosphokinase
	*Direct bilirubin will only be tested in instances where total bilirubin is elevated. Direct bilirubin will be measured automatically by the central lab on the sample where total bilirubin is elevated. An additional sample is not required to be collected.

Hematology	Hemoglobin (including mean corpuscular volume), mean corpuscular hemoglobin, mean corpuscular hemoglobin concentration, hematocrit, red blood cell count, total white blood cell count, platelet count Differential blood counts, including basophils, eosinophils, neutrophils, lymphocytes, and monocytes
Urinalysis	Leukocytes, blood, nitrite, protein, urobilinogen, bilirubin, pH, specific gravity, ketones, glucose If there is a clinically significant positive result, urine will be sent for microscopy and/or culture.
Pregnancy	Serum beta human chorionic gonadotropin (all female patients of child-bearing potential), serum follicle-stimulating hormone (suspected postmenopausal female patients only [defined in Section 5.5.1]), urine pregnancy test (as required by local regulations)
Serology testing	Hepatitis B surface antigen, hepatitis C virus antibody, HIV-1/HIV-2 antibodies; tuberculosis will also be tested locally by QuantiFERON-TB Gold at Italian sites only (Appendix 2). Patients with a known history of hepatitis infection must be tested to confirm active infection. All patients will be tested for hepatitis B surface antigen and, if positive, will not be allowed to enroll in the study. All patients will also be tested for hepatitis C antibody and, if positive, should be tested for viral RNA. If the viral RNA test is negative, indicating inactive/resolved hepatitis C infection, then the patient can enroll in the study as long as their liver panel is within range of the inclusion and exclusion criteria (Section 4.1). If the viral RNA test is positive, indicating active viral hepatitis C, the patient will not be allowed to enroll in the study.

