8. GENERAL CONSIDERATIONS FOR DATA ANALYSES

8.1 STANDARD SUMMARY STATISTICS

Continuous data will be summarized using descriptive statistics (n, mean, standard deviation (SD), standard error (SE), median, first quartile, third quartile, minimum, and maximum). Categorical data will be summarized using the count and percentage in each category. When count data are presented, in cases where the count is zero, the percentage will not be displayed, in order to draw attention to the non-zero counts. A row denoted 'Missing' will be included in count tabulations where specified on the shells to account for dropouts and missing values. The denominator for all percentages will usually be the number of patients in that treatment group within the analysis set of interest (i.e., including patients with missing data). Exceptions to this are when binary or categorical variables are derived from changes from baseline, where the denominator is all patients within the analysis set of interest with non-missing baseline. . Percentages will be displayed to 1 decimal place, except in the case of 100% which will be presented with no decimal places.

For the summary statistics of all numerical variables unless otherwise specified, minimum and maximum will be displayed to the same level of precision as reported in the raw data. Mean, median, quartiles, 95% CI, SD and SE will be displayed to one level of precision greater than the data collected. P-values will be rounded to four decimal places. A p-value below 0.0001 will be reported as "<0.0001." A p-value above 0.9999 will be reported as ">0.9999". Data will be presented in summary tables, listings, and figures. Where appropriate, an estimation approach will be taken, and point estimates and confidence intervals (CIs) of interest will be constructed. Patients will be identified in the listings by patient identification number. Summary statistics will be presented by treatment arm and/or overall (if required). In the case where the number of patients included in an analysis is 0, no statistics will be presented; if only one patient is included, then only n, and mean will be presented.

All analyses will be conducted using SAS® Version 9.4 or higher.

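### No planned laboratory table counts, by arm, the patients whose worst post-baseline creatinine or creatine phosphokinase went high

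*SAP*

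**What the plan says.** Protocol 6.1.5, Table 6, puts both analytes in the required serum chemistry panel; the relevant part of the row reads "creatinine, total bilirubin, direct bilirubin*, alkaline phosphatase, aspartate aminotransferase, alanine aminotransferase, gamma-glutamyltransferase, creatine phosphokinase".

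SAP 10.3.5 plans three laboratory outputs:

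- **By-visit tables for all laboratory data**, in which "absolute values and change from baseline will be summarized with standard summary statistics (see Section 8.1), by treatment group". SAP 8.1 defines these statistics: "Continuous data will be summarized using descriptive statistics (n, mean, standard deviation (SD), standard error (SE), median, first quartile, third quartile, minimum, and maximum".
- **Shift tables for a named list only**, showing "the shift from baseline category to (a) lowest post-baseline category; and (b) highest post-baseline category". For chemistry and urinalysis the list is "biochemistry (total bilirubin, alkaline phosphatase, aspartate aminotransferase, alanine aminotransferase, gamma-glutamyltransferase), and urinalysis (glucose, blood and protein) parameters". Nine hematology parameters are also listed.
- **Listings** of all results, in which each patient's three highest and three lowest out-of-range values are flagged, with unscheduled and early termination results taken into account.

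SAP 10.3 adds: "Safety data collected at unscheduled visits and local laboratory data will be excluded from by-visit summaries using descriptive statistics". The same sentence keeps those results for listings and for finding worst values.

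The protocol mentions both analytes outside the panel. On creatinine, Section 1.3.5.1 says: "A small increase in (model-adjusted geometric mean) serum creatinine in the combined losmapimod group compared to placebo at Week 12 was noted". On CPK, Section 5.8, repeated in Appendix 3, says: "Particular attention should be paid to creatine phosphokinase (already part of the laboratory safety monitoring) in patients who start treatment with a statin".

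**The concern.** For renal and muscle safety, one question is how many patients on each arm went from an acceptable value to a high one at any time on treatment. A worst-value shift table answers that directly and is the laboratory output that draws on unscheduled results. Leaving creatinine and CPK off the list removes that answer for two analytes to which the protocol itself draws attention.

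The study report could then describe both analytes through visit-level statistics alone. A reader who wanted the number of affected patients per arm would have to count them by hand from listings.

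**Working it through.** No arithmetic is needed for the main point. The check compares the list with the panel and follows a high value through the planned outputs.

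**1. Panel against list.** Table 6 names 16 serum chemistry analytes: glucose, sodium, potassium, calcium, inorganic phosphate, total protein, albumin, blood urea nitrogen, creatinine, total bilirubin, direct bilirubin, alkaline phosphatase, AST, ALT, gamma-glutamyltransferase and CPK. Five are in the shift list, all liver tests. Creatinine and CPK are among the other 16 − 5 = 11.

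**2. Why these two.** Section 1.3.5.1 gives a Week 12 creatinine ratio to placebo of 1.07 (95% CI 1.02 to 1.11) in one study and 1.01 to 1.07 in three other Phase 2 studies. Sections 5.8 and Appendix 3 ask for attention to CPK in patients who start a statin, and Appendix 3 puts statins first among the drugs that may affect muscle function.

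**3. Where a high value goes.**

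| Source of the value | By-visit table | Worst-value shift: liver tests | Worst-value shift: creatinine, CPK | Listing |
|---|---|---|---|---|
| Scheduled visit | Yes | Yes | None planned | Yes |
| Early termination or safety follow-up | Yes, if selected by windowing (9.5.1) or at the follow-up timepoint | Yes | None planned | Yes |
| Unscheduled visit | No (9.5.2, 10.3) | Yes (10.3) | None planned | Yes |
| Local laboratory | No (10.3) | Yes (10.3) | None planned | Yes |

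For creatinine and CPK the last two rows contain no laboratory table at all.

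**4. What the by-visit table can show.** It gives one maximum value and one maximum change per arm per visit. An arm with one high patient and an arm with ten can have the same maximum. The third quartile responds only when many patients are affected: with 115 per arm, 115 × 0.25 = 28.75, so up to 28 patients could be above the ULN at a visit while the third quartile stays in range. The mean and SD would move, but neither gives a count. Visit tables also cannot be added up into patients who were ever high, because the same patient may or may not recur.

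**5. Why unscheduled values matter.** Protocol 6.1.5 requires clinically significant abnormal results to be repeated until they settle. From Week 12 the scheduled days are 84, 168, 252 and 336, a gap of 84 days each time. Repeat tests can therefore fall between scheduled visits, and a peak found on repeat would be listed but not tabulated.

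**6. The adverse event route.** Protocol 6.1.5 has clinically significant results recorded as adverse events, but exempts findings linked to the underlying disease unless they are worse than expected for the patient. In a muscular dystrophy a CPK rise can readily be attributed to the disease. Protocol 7.7 states the recording rule without the exemption, so this route is least certain for CPK.

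**7. Practice elsewhere in the SAP.** Patient counts by extreme on-treatment value are planned for vital signs and body weight (10.3.6) and QTcF (10.3.7). Liver tests also get counts by multiples of ULN (10.3.4). The SAP gives no reason for treating creatinine and CPK differently.

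**The case against.** The case for leaving the plan alone is substantial.

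- Protocol 9.1.6.7 promises only descriptive summaries of laboratory change over time, and SAP 10.3.5 delivers that for both analytes. Aiming the chemistry shift tables at liver tests fits the protocol's only event of special interest (7.5).
- The CPK sentence is an instruction for monitoring patients who start a statin. It sets no analysis requirement.
- Section 1.3.5.1 also says that the creatinine rise appeared to lessen with continued treatment and after stopping, that renal insufficiency was not more frequent, and that the sponsor's own studies showed no creatinine change of clinical relevance.
- The listings flag extremes for every analyte, unscheduled results included, and significant rises can reach the adverse event tables by arm and maximum grade (10.3.1).

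All of this stands, and it rules out three stronger readings. A reader might infer that individual rises in these analytes appear in no laboratory table. That is wrong: the largest scheduled value and the largest change per arm are shown at each visit, and windowing can bring in early termination values. A reader might infer that a modest overall creatinine shift, such as the 1.07 ratio, would go unseen. It would not: a shift of the whole distribution is what by-visit means and medians show best, and a count of patients above normal would be the less sensitive measure. A reader might also infer that the SAP departs from the protocol, or that the documents point to a renal or muscle safety problem. They support neither.

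What the objection does not supply is a per-arm count of patients with a high worst value. A maximum is one patient, a flagged listing compares nothing between arms, and the adverse event tables depend on investigator judgment and on the exemption for disease-related findings.

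**Conclusion.** The gap is real but small. As the SAP is written, no laboratory table counts patients by arm according to their worst post-baseline creatinine or CPK, and unscheduled and local results for these two analytes enter no laboratory table. No numerical effect on the trial's conclusions can be stated, and none is claimed; the primary analysis, the testing sequence and the power are unaffected. This is an inexpensive improvement to safety reporting, not an error to be corrected before the trial can be interpreted.

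The conclusion rests on the SAP text. The table shells that Appendix A cites are a separate file and were not available; if they already include these analytes, the SAP wording should be brought into line. That CPK may already be raised at baseline is an assumption, since the documents give no baseline CPK values.

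**What to change.** In SAP 10.3.5, add creatinine and creatine phosphokinase to the biochemistry shift list. State that the worst post-baseline value is used with unscheduled results included, as SAP 10.3 already provides for worst-value analyses.

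For CPK, also tabulate the number and percentage of patients per arm by worst post-baseline value in multiples of ULN, with the categories fixed before unblinding. If many patients start above normal, a low/normal/high shift would say little. SAP 10.3.4 already counts patients by ULN multiples for the liver tests, although by visit, so the format is familiar.

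The cost is two parameters in an existing table and one small additional CPK table. No new data are collected, and no efficacy analysis or significance level changes.
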